6.3.9 Cytokine-Release Syndrome

No premedication is indicated for the administration of Cycle 1 of atezolizumab or tiragolumab. However, patients who experience CRS with atezolizumab or tiragolumab may receive premedication with antihistamines, anti-pyretics, and/or analgesics (e.g., acetaminophen) for subsequent infusions.

CRS is defined as a supraphysiologic response following administration of any immune therapy that results in activation or engagement of endogenous or infused T cells and/or other immune effector cells. Symptoms can be progressive, always include fever at the onset, and may include hypotension, capillary leak (hypoxia), and end-organ dysfunction (Lee et al. 2019). CRS has been well documented with chimeric antigen receptor T-cell therapies and bispecific T-cell engager antibody therapies but has also been reported with immunotherapies that target PD-1 or PD-L1 (Rotz et al. 2017; Adashek and Feldman 2019), including atezolizumab.

Severe SARS CoV 2 infection is associated with a CRS involving the inflammatory cytokines interleukin (IL)-6, IL-10, IL-2, and IFN- γ (Merad and Martin 2020). If a patient develops suspected CRS during the study, a differential diagnosis should include SARS CoV 2 infection, which should be confirmed or refuted through assessment of exposure history, appropriate laboratory testing, and clinical or radiologic evaluations per investigator's judgment. If a diagnosis of SARS CoV 2 infection is confirmed, the disease should be managed as per local or institutional guidelines.

Guidelines for medical management of CRS are provided in the table below.

Management Guidelines for Infusion-Related Reactions and Cytokine-Release Syndrome

| Event | Management |
|---|--|
| Grade 1 ^a fever ^b with or without constitutional symptoms | 
 ● Immediately interrupt infusion. ● Upon symptom resolution, wait for 30 minutes and then restart infusion at half the rate being given at the time of event onset. ● If the infusion is tolerated at the reduced rate for 30 minutes, the infusion rate may be increased to the original rate. ● If symptoms recur, discontinue infusion of this dose. ● Administer symptomatic treatment,^c including maintenance of IV fluids for hydration. ● In case of rapid decline or prolonged CRS (> 2 days) or in patients with significant symptoms and/or comorbidities, consider managing as per Grade 2. ● For subsequent infusions, consider administration of oral premedication with antihistamines, antipyretic medications, and/or analgesics, and monitor closely for CRS. |
| Grade 2 ^a fever ^b with at least one of the | 
 ● Immediately interrupt infusion. ● Upon symptom resolution, wait for 30 minutes and then restart infusion at half the rate being given at the time of event onset. |

| Event | Management |
|---|--|
| 
following: Hypotension not requiring vasopressors Hypoxia requiring low-flow oxygen^d by nasal cannula or blow-by
 | 
 ● If symptoms recur, discontinue infusion of this dose. ● Administer symptomatic treatment.^c ● For hypotension, administer IV fluid bolus as needed. ● Monitor cardiopulmonary and other organ function closely (in the ICU, if appropriate). Administer IV fluids as clinically indicated, and manage constitutional symptoms and organ toxicities as per institutional practice. ● Rule out other inflammatory conditions that can mimic CRS (e.g., sepsis). If no improvement within 24 hours, initiate workup and assess for signs and symptoms of HLH or MAS as described in this appendix. ● Consider IV corticosteroids (e.g., methylprednisolone 2 mg/kg/day or dexamethasone 10 mg every 6 hours). ● Consider anti-cytokine therapy. ● Consider hospitalization until complete resolution of symptoms. If no improvement within 24 hours, manage as per Grade 3, that is, hospitalize patient (monitoring in the ICU is recommended), permanently discontinue atezolizumab or tiragolumab, and contact Medical Monitor. ● If symptoms resolve to Grade 1 or better for 3 consecutive days, the next dose of atezolizumab or tiragolumab may be administered. For subsequent infusions, consider administration of oral premedication with antihistamines, antipyretic medications, and/or analgesics and monitor closely for CRS. ● If symptoms do not resolve to Grade 1 or better for 3 consecutive days, contact PI. |
| 
Grade 3^a Fever^b with at least one of the following:
 
 ● Hypotension requiring a vasopressor (with or without vasopressin) ● Hypoxia requiring high-flow oxygen^d by nasal cannula, face mask, non-rebreather mask, or Venturi mask | 
 ● Permanently discontinue atezolizumab or tiragolumab and contact Medical Monitor.^c ● Administer symptomatic treatment.^c ● For hypotension, administer IV fluid bolus and vasopressor as needed. ● Monitor cardiopulmonary and other organ function closely; monitoring in the ICU is recommended. Administer IV fluids as clinically indicated, and manage constitutional symptoms and organ toxicities as per institutional practice. ● Rule out other inflammatory conditions that can mimic CRS (e.g., sepsis). If no improvement within 24 hours, initiate workup and assess for signs and symptoms of HLH or MAS as described in this appendix. ● Administer IV corticosteroids (e.g., methylprednisolone 2 mg/kg/day or dexamethasone 10 mg every 6 hours). ● Consider anti-cytokine therapy. ● Hospitalize patient until complete resolution of symptoms. If no improvement within 24 hours, manage as per Grade 4, that is, admit patient to ICU and initiate hemodynamic monitoring, mechanical ventilation, and/or IV fluids and vasopressors as needed; for patients who are refractory to anti-cytokine therapy, experimental treatments may be considered at the discretion of the investigator and in consultation with the PI. |
| 
Grade 4^a
 | 
 ● Permanently discontinue atezolizumab or tiragolumab and contact PI.^f |

| Event | Management |
|--|---|
| Fever ^b with at least one of the following: 
 ● Hypotension requiring multiple vasopressors (excluding vasopressin) ● Hypoxia requiring oxygen by positive pressure (e.g., CPAP, BiPAP, intubation and mechanical ventilation) | 
 ● Administer symptomatic treatment.^c ● Admit patient to ICU and initiate hemodynamic monitoring, mechanical ventilation, and/or IV fluids and vasopressors as needed. Monitor other organ function closely. Manage constitutional symptoms and organ toxicities as per institutional practice. ● Rule out other inflammatory conditions that can mimic CRS (e.g., sepsis). If no improvement within 24 hours, initiate workup and assess for signs and symptoms of HLH or MAS as described in this appendix. ● Administer IV corticosteroids (e.g., methylprednisolone 2 mg/kg/day or dexamethasone 10 mg every 6 hours). ● Consider anti-cytokine therapy. For patients who are refractory to anti-cytokine therapy, experimental treatments^f may be considered at the discretion of the investigator and in consultation with the PI. ● Hospitalize patient until complete resolution of symptoms. |

ASTCT = American Society for Transplantation and Cellular Therapy; BiPAP = bi-level positive airway pressure; CAR = chimeric antigen receptor; CPAP = continuous positive airway pressure; CRS = cytokine-release syndrome; CTCAE = Common Terminology Criteria for Adverse Events; eCRF = electronic Case Report Form; HLH = hemophagocytic lymphohistiocytosis; ICU = intensive care unit; MAS = macrophage activation syndrome; NCCN = National Cancer Comprehensive Network; NCI = National Cancer Institute.

The management guidelines have been adapted from the NCCN guidelines for the management of CAR T-cell–related toxicities (Version 2.2019).

^a Grading system for management guidelines is based on the ASTCT CRS Consensus Grading Scale. NCI CTCAE v5.0 and the ASTCT CRS Consensus Grading Scale should be used when reporting severity of CRS on the Adverse Event eCRF. NCI CTCAE v5.0 should be used when reporting severity of organ toxicities associated with CRS on the dedicated Cytokine Release Syndrome eCRF. Organ toxicities associated with CRS should not influence overall CRS grading.

^b Fever is defined as temperature $\geq 38^{\circ}\text{C}$ not attributable to any other cause. In patients who develop CRS and then receive anti-pyretic, anti-cytokine, or corticosteroid therapy, fever is no longer required when subsequently determining event severity (grade). In this case, the grade is driven by the presence of hypotension and/or hypoxia.

^c Symptomatic treatment may include oral or IV antihistamines, antipyretic medications, analgesics, bronchodilators, and/or oxygen. For bronchospasm, urticaria, or dyspnea, additional treatment may be administered as per institutional practice.

^d Low flow is defined as oxygen delivered at ≤ 6 L/min, and high flow is defined as oxygen delivered at > 6 L/min.

^e Resumption of atezolizumab or tiragolumab may be considered in patients who are deriving benefit and have fully recovered from the event. The decision to re-challenge patients with atezolizumab or tiragolumab should be based on the investigator’s benefit-risk assessment and documented by the investigator. The Medical Monitor is available to advise is needed. For subsequent infusions, administer oral premedication with antihistamines, antipyretics medications, and/or analgesics, and monitor closely for CRS. Premedication with corticosteroids and extending the infusion time may also be considered after consulting the PI and considering the benefit–risk ratio.

^f Refer to Riegler et al. (2019)

6.3.10 Pancreatic Events

The differential diagnosis of acute abdominal pain should include pancreatitis. Appropriate workup should include an evaluation for ductal obstruction, as well as

serum amylase and lipase tests. Management guidelines for pancreatic events, including pancreatitis, are provided in the table below.

Management Guidelines for Pancreatic Events, Including Pancreatitis

| Event | Management |
|---|---|
| Amylase and/or lipase elevation, Grade 2 | 
Amylase and/or lipase > 1.5-2.0 · ULN:
 
 ● Continue atezolizumab and tiragolumab. ● Monitor amylase and lipase weekly. ● For prolonged elevation (e.g., > 3 weeks), consider treatment with corticosteroids equivalent to 10 mg/day oral prednisone. 
Asymptomatic with amylase and/or lipase > 2.0-5.0 · ULN:
 
 ● Treat as a Grade 3 event. |
| Amylase and/or lipase elevation, Grade 3 or 4 | 
 ● Withhold atezolizumab and tiragolumab for up to 12 weeks after event onset.^a ● Refer patient to GI specialist. ● Monitor amylase and lipase every other day. ● If no improvement, consider treatment with corticosteroids equivalent to 1-2 mg/kg/day oral prednisone. ● If event resolves to Grade 1 or better, resume atezolizumab and tiragolumab.^b ● If event does not resolve to Grade 1 or better while withholding atezolizumab and tiragolumab, permanently discontinue atezolizumab and tiragolumab and contact PI.^c ● For recurrent events, permanently discontinue atezolizumab and tiragolumab and contact PI.^c |
| Immune-mediated pancreatitis, Grade 2 or 3 | 
 ● Withhold atezolizumab and tiragolumab for up to 12 weeks after event onset.^a ● Refer patient to GI specialist. ● Initiate treatment with corticosteroids equivalent to 1-2 mg/kg/day IV methylprednisolone and convert to 1-2 mg/kg/day oral prednisone or equivalent upon improvement. ● If event resolves to Grade 1 or better, resume atezolizumab and tiragolumab.^b ● If event does not resolve to Grade 1 or better while withholding atezolizumab and tiragolumab, permanently discontinue atezolizumab and tiragolumab and contact PI.^c ● For recurrent events, permanently discontinue atezolizumab and tiragolumab and contact PI.^c |
| Immune-mediated pancreatitis, Grade 4 | 
 ● Permanently discontinue atezolizumab and tiragolumab and contact PI.^c ● Refer patient to GI specialist. ● Initiate treatment with corticosteroids equivalent to 1-2 mg/kg/day IV methylprednisolone and convert to 1-2 mg/kg/day oral prednisone or equivalent upon improvement. ● If event does not improve within 48 hours after initiating corticosteroids, consider adding an immunosuppressive agent. ● If event resolves to Grade 1 or better, taper corticosteroids over ≥ 1 |

| Event | Management |
|-------|------------|
| | month. |

GI = gastrointestinal; ULN=upper limit of normal.

- ^a Atezolizumab and tiragolumab may be withheld for a longer period of time (i.e., > 12 weeks after event onset) to allow for corticosteroids (if initiated) to be reduced to the equivalent of ≤ 10 mg/day oral prednisone. The acceptable length of the extended period of time must be based on the investigator's benefit-risk assessment and in alignment with the protocol requirements for the duration of treatment and documented by the investigator.
- ^b If corticosteroids have been initiated, they must be tapered over ≥ 1 month to the equivalent of ≤ 10 mg/day oral prednisone before atezolizumab and tiragolumab can be resumed.
- ^c Resumption of atezolizumab and tiragolumab may be considered in patients who are deriving benefit and have fully recovered from the immune-mediated event. The decision to re-challenge patients with atezolizumab should be based on the investigator's benefit-risk assessment and documented by the investigator.

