| To determine the relapse-free survival in patients with stage II melanoma who test positive for circulating tumor DNA and are treated with atezolizumab and tiragolumab, and those who are treated with atezolizumab alone | Relapse-free survival (RFS), defined as the duration of time from the date of randomization to the date of earliest disease relapse or death, whichever occurs first. | RFS is an acceptable measure of clinical benefit for a late stage study that demonstrates superiority of a new antineoplastic therapy, especially if the magnitude of the effect is large and the therapy has an acceptable risk/benefit profile. |
| To determine the distant metastasis-free survival in patients with stage II melanoma who test positive for circulating tumor DNA and are treated with atezolizumab and tiragolumab, and those who are treated with atezolizumab alone (both circulating tumor DNA positive and negative). | Distant-metastasis free survival (DMFS), defined as the duration of time from the date of positive ctDNA being confirmed to the date of appearance of a distant metastasis or death, whichever occurs first. | The secondary efficacy objective of this study is to compare DMFS between the two treatment arms |
| To determine the overall survival of patients with stage II melanoma. | Overall survival (OS), defined as the duration of time from the date of positive ctDNA being confirmed to death from any cause. | The secondary efficacy objective of this study is to compare OS between the two treatment arms |
| To evaluate the safety and tolerability of atezolizumab | Defined as the number of treatment-related grade 3 or | Safety parameters commonly used for |

| | | |
|--|--|--|
| and tiragolumab in patients with stage II melanoma. | greater AEs and discontinuations due to treatment-related AEs. | evaluating investigational systemic anticancer treatments are included as safety endpoints including, but not limited to, the incidence of, causality, and outcome of AEs/serious adverse events (SAEs); and changes in vital signs and laboratory values. Adverse events will be assessed as defined by CTCAE, Version 5.0. |
| To assess the impact of ctDNA kinetics on outcomes (relapse-free survival, distant metastasis-free survival, and overall survival) in patients with surgically resected stage II melanoma. | | |

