6.2.1 Study treatment discontinuation criteria specific to tiragolumab or atezolizumab-related AEs

- Any Grade ≥ 2 treatment-related uveitis, eye pain, or blurred vision that does not respond to topical therapy and does not improve to Grade 1 severity within 8 weeks or requires systemic treatment.

- Any Grade ≥ 2 treatment-related pneumonitis or interstitial lung disease that does not resolve following dose delay and systemic steroids.
- For Grade ≥ 3 adrenal insufficiency or Grade ≥ 4 hypophysitis, treatment needs to be discontinued regardless of control with hormone replacement (Note: Hospitalization for diagnostic workup of adrenal insufficiency without severe symptoms should not require discontinuation).
- Any Grade ≥ 3 non-skin, treatment-related AE lasting > 7 days or recurs, with the following exceptions for uveitis, pneumonitis, bronchospasm, diarrhea, colitis, neurologic toxicity, hypersensitivity reactions, infusion reactions, endocrinopathies, and laboratory abnormalities:
 - Grade 3 treatment-related uveitis, pneumonitis, bronchospasm, diarrhea, colitis, neurologic toxicity, hypersensitivity reaction, or infusion reaction of any duration requires discontinuation.
 - Grade 3 treatment-related endocrinopathies (excluding adrenal insufficiency and hypophysitis) adequately controlled with only physiologic hormone replacement do not require discontinuation.
 - Grade 3 treatment-related laboratory abnormalities do not require treatment discontinuation except:
 - Grade 3 treatment-related thrombocytopenia > 7 days or associated with clinically significant bleeding requires discontinuation.
- In most cases of Grade 3 AST or ALT elevation, study treatment will be permanently discontinued. If the Investigator determines a possible favorable benefit/risk ratio that warrants continuation of study treatment, a discussion between the Investigator and the Medical Monitor/designee must occur.
- Any treatment-related liver function test abnormality that meets the following criteria require discontinuation:
 - AST or ALT $> 5 \times$ ULN to $8 \times$ ULN for > 2 weeks
 - AST or ALT $> 8 \times$ ULN
 - Total bilirubin $> 5 \times$ ULN
 - Concurrent AST or ALT $> 3 \times$ ULN and total bilirubin $> 2 \times$ ULN
- Grade 3 or 4 infusion reaction of any duration
- Any Grade 4 treatment -related AE or laboratory abnormality, except for the following events, which do not require discontinuation:
 - Grade 4 neutropenia ≤ 7 days.

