 - Grade 4 lymphopenia or leukopenia ≤ 14 days in duration.
 - Isolated Grade 4 amylase or lipase abnormalities that are not associated with symptoms or clinical manifestations of pancreatitis and decrease to Grade < 4 or return to baseline within 7 days.
 - Isolated Grade 4 electrolyte imbalances/abnormalities that are not associated with clinical sequelae and are corrected with supplementation/appropriate management within 72 hours of their onset.
 - Grade 4 treatment -related endocrinopathy AEs (except adrenal insufficiency or hypophysitis), such as hyper- or hypothyroidism, or glucose intolerance, which resolve or are adequately controlled with physiologic hormone replacement (corticosteroids at ≤ 10 mg of prednisone or equivalent per day, thyroid hormones) or glucose-controlling agents,

respectively, may not require discontinuation after discussion with and approval from the Medical Monitor.

- Any AE, laboratory abnormality, or intercurrent illness that, in the judgment of the Investigator, presents a substantial clinical risk to the patient with continued treatment.
- Disease recurrence (local, regional, or distant), including new primary melanoma (except MMIS Stage 0) Note: Non-melanoma skin cancer does not require treatment discontinuation. In the absence of intolerable toxicity, patients with diagnosed MMIS Stage 0 melanoma will be eligible to continue study treatment using the same dose and schedule for their original melanoma of up to approximately 1 year of study treatment starting from first dose, at the discretion of the Investigator.

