6.3.14 Renal and Urinary Disorders

Eligible patients must have adequate renal function. Renal function, including serum creatinine, should be monitored throughout study treatment. Patients with abnormal renal function should be evaluated and treated for other more common etiologies (including prerenal and postrenal causes, and concomitant medications such as nonsteroidal anti-inflammatory drugs). Refer the patient to a renal specialist if clinically indicated. A renal biopsy may be required to enable a definitive diagnosis and appropriate treatment.

Patients with signs and symptoms of nephritis, in the absence of an identified alternate etiology, should be treated according to the guidelines in the table below.

Management Guidelines for Renal Events

| Event | Management |
|----------------------|--|
| Renal event, Grade 1 | 
 ● Continue atezolizumab and tiragolumab. ● Monitor kidney function, including creatinine, closely until values resolve to within normal limits or to baseline values. |

| Event | Management |
|---------------------------|--|
| Renal event, Grade 2 | 
 ● Withhold atezolizumab and tiragolumab for up to 12 weeks after event onset.^a ● Refer patient to renal specialist. ● Initiate treatment with corticosteroids equivalent to 1-2 mg/kg/day oral prednisone. ● If event resolves to Grade 1 or better, resume atezolizumab and tiragolumab.^b ● If event does not resolve to Grade 1 or better while withholding atezolizumab and tiragolumab, permanently discontinue atezolizumab and tiragolumab and contact PI.^c |
| Renal event, Grade 3 or 4 | 
 ● Permanently discontinue atezolizumab and tiragolumab and contact PI. ● Refer patient to renal specialist and consider renal biopsy. ● Initiate treatment with corticosteroids equivalent to 1-2 mg/kg/day oral prednisone. ● If event does not improve within 48 hours after initiating corticosteroids, consider adding an immunosuppressive agent. ● If event resolves to Grade 1 or better, taper corticosteroids over ≥ 1 month. |

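### Sections 6.2.1 and 6.3.10 contradict each other, in both directions, on when amylase or lipase elevations end treatment, and no text says which prevails

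*Combined protocol and SAP*

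**What the plan says.** **Section 6.2.1 (discontinuation criteria).** The general trigger is a Grade 3 or higher "non-skin, treatment-related AE lasting > 7 days or recurs, with the following exceptions", and laboratory abnormalities are among the exceptions. A sub-bullet adds: "Grade 3 treatment-related laboratory abnormalities do not require treatment discontinuation except". Thrombocytopenia is the only exception listed there; AST/ALT and other liver tests have their own bullets. Grade 4 events and laboratory abnormalities do require discontinuation, apart from a short list. That list includes "Isolated Grade 4 amylase or lipase abnormalities that are not associated with symptoms or clinical manifestations of pancreatitis", provided the value falls below Grade 4 or returns to baseline within 7 days.

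**Section 6.3.10 (pancreatic table).** A Grade 3 or 4 amylase or lipase elevation is held for up to 12 weeks and treatment resumes at Grade 1 or better. Two bullets end treatment: "If event does not resolve to Grade 1 or better while withholding atezolizumab and tiragolumab, permanently discontinue atezolizumab and tiragolumab and contact PI", and "For recurrent events, permanently discontinue atezolizumab and tiragolumab and contact PI". Both carry footnote c, under which resumption may be considered after full recovery. In the Grade 2 row, asymptomatic values above 2 and up to 5 x ULN carry the instruction "Treat as a Grade 3 event".

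**Section 6.3.14 (renal table).** The Grade 3 or 4 row says to "permanently discontinue atezolizumab and tiragolumab and contact PI", without footnote c. The table is introduced for patients with signs and symptoms of nephritis.

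**Endpoint.** Section 2.0 defines safety by treatment-related Grade 3 or "greater AEs and discontinuations due to treatment-related AEs". Section 14.3 and the Protocol Summary list only the Grade 3 or higher events.

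**The concern.** Both sections tell the site when to stop, both name amylase and lipase, and for several results they give different answers. Section 6.0 only lets the PI make further holds and modifications; it does not rank the two.

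The Schedule of Activities draws amylase, lipase and the CMP on Day 1 of every cycle, for up to 13 cycles, and the trial is multicenter. The same laboratory result could therefore end adjuvant treatment at one site and not at another. Exposure would then vary for a reason unrelated to the patient, and the Section 2.0 count of discontinuations would partly reflect which page was read.

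**Working it through.** The main check is a comparison of texts. It assumes that the elevation is judged treatment-related, because 6.2.1 is limited to such events.

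| Result | 6.2.1 | 6.3.10 or 6.3.14 | Agree? |
|---|---|---|---|
| Grade 3 amylase/lipase, recurrent | Discontinuation not required | Permanent discontinuation, PI contact, footnote c | No |
| Grade 3 amylase/lipase, not down to Grade 1 during the hold | Discontinuation not required | Same as above | No |
| Asymptomatic >2 to 5 x ULN, recurrent or unresolved | Not named; exempt by implication, since even Grade 3 is exempt | Handled as Grade 3, so same as above | No, by implication |
| Isolated asymptomatic Grade 4, below Grade 4 within 7 days, but recurrent or never at Grade 1 | Exempt | Permanent discontinuation, PI contact, footnote c | No |
| Isolated Grade 4, still Grade 4 and not at baseline after 7 days | Discontinuation | Hold up to 12 weeks; resume at Grade 1 or better | No, in the opposite direction |
| Isolated Grade 3 creatinine rise | Discontinuation not required | Permanent discontinuation, if it counts as a renal event | Depends on scope |
| Grade 4 renal event | Discontinuation | Permanent discontinuation | Yes |

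In the first four rows the table is the stricter text. In the fifth, 6.2.1 is stricter: a persistent Grade 4 value falls outside its 7-day exemption and back under its general Grade 4 rule.

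**Bearing on the primary endpoint.** Section 5.3 replaces patients who stop before C3D1 in stage 1 but not in stage 2. With the Section 14.5 cut-offs (at least 3 of 18, then at least 8 overall), the chance of a promising result when k stage 2 patients are lost is

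P = Σ (x = 3 to 18) Pr[Bin(18, p) = x] × Pr[Bin(25 − k, p) ≥ 8 − x].

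- Plan as written, k = 0: 0.0480 at p = 0.10 and 0.8003 at p = 0.25, matching the stated alpha of 0.05 and power of 0.8.
- k = 1, p = 0.25: 0.7889.
- k = 2, p = 0.25: 0.7757.

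Each stage 2 patient lost before C3D1 thus costs a little over one percentage point of power. Few losses are likely by this route. A recurrence needs an elevation, a hold, recovery and a second elevation. After an elevation at C2D1 and resumed Cycle 2 dosing, the next scheduled Day 1 draw is C3D1 itself.

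**The case against.** The strongest reply is that the two sections can be followed together. Saying that discontinuation is not required does not forbid it, so a site that follows 6.3.10 breaches nothing in 6.2.1. At a first Grade 3 elevation the two are compatible, because 6.3.10 only holds and 6.2.1 sets no hold rule for these results. Section 6.2.1 also lets the investigator stop for any laboratory abnormality that poses a substantial clinical risk. The pancreatic stop bullets call for PI contact, which should limit differences between sites.

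This stands for first events that resolve. It does not settle recurrence or non-resolution: 6.3.10 directs a stop there, while 6.2.1 takes laboratory abnormalities out of its own recurrence trigger. A site relying on 6.2.1 would continue and have no prompt to call the PI. Nor does the reply reach persistent Grade 4 values, where 6.2.1 is the mandatory text.

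Some stronger readings are tempting but unsupported:

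- **That a second asymptomatic value above 2 x ULN ends both drugs for good.** Footnote c lets re-challenge be considered after full recovery, and 6.2.1 exempts these Grade 2 values only by implication.
- **That the table is always the stricter text.** The persistent Grade 4 case shows otherwise.
- **That 6.3.14 contradicts 6.2.1 on laboratory changes generally.** The renal table is introduced for signs and symptoms of nephritis, and Grade 4 agrees. Only an isolated Grade 3 creatinine rise could conflict. That reading is possible because the rows are headed as renal events and the Grade 1 row tracks creatinine, but it is secondary.
- **That the two recovery criteria compete.** The 7-day condition in 6.2.1 decides whether the exemption applies; it is not a condition for resuming dosing.

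**Conclusion.** The contradiction between 6.2.1 and 6.3.10 is real, runs in both directions and is not resolved elsewhere in the document. It should be corrected because it bears on patient management and exposure at routinely scheduled visits.

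Its size cannot be estimated, since the documents give no incidence of amylase, lipase or creatinine elevation. A reader might infer a number by assuming that each of the 12 Day 1 draws from C2 to C13 independently exceeds 2 x ULN with probability 1% to 5%. The chance of two or more, 1 − (1 − p)^12 − 12p(1 − p)^11, is then 0.6% to 11.8%. That range should not be read as a forecast. Two high draws may be one persistent event, a hold interrupts the schedule, not every patient completes 13 cycles, and the threshold also captures persistent Grade 4 values for which 6.2.1 itself requires a stop.

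The consequence for endpoints is limited. Discontinuations count as an endpoint in Section 2.0 only. The stopping rule in 14.7.1 counts Grade 3 or higher treatment-related events, not discontinuations, and Section 14.7 treats all analyses as exploratory. Any effect on ctDNA clearance at C3D1 is likely small.

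**What to change.** Reconcile 6.2.1 with 6.3.10 so that each of these cases has one action: asymptomatic amylase or lipase above 2 and up to 5 x ULN; Grade 3; isolated Grade 4, both within and beyond 7 days; non-resolution during a hold; and recurrence. State which section prevails, or cross-refer them so that neither can be applied alone. State whether an isolated creatinine rise falls under 6.3.14. The Section 2.0 discontinuation count would then rest on one rule. Which rule stands is for the sponsor's clinicians.

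The cost is a wording amendment with IRB review. It needs no extra patients, tests or analyses.
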